**Study Design:**

This is a Phase 1/2a, open-label study of BMS-986016 administered as a single agent and in combination with nivolumab to subjects with advanced solid tumors.

**Part A and Part B** consist of a 3 + 3 + 3 dose escalation design and, implemented in site-specific amendment #15 (dated 13 August 2018) and superseding the 3 + 3+ 3 dose escalation design, the Bayesian Logistic Regression Model (BLRM)-Copula design (for Part B only), evaluating BMS-986016 administered as a single agent (Part A) or in combination with nivolumab (Part B) as sequential infusions in subjects with advanced solid tumors. Treatment in Part B will be initiated upon the decision to escalate to the third dose cohort in Part A (in accordance with dose escalation rules); subsequently, escalation in the 2 parts will proceed in parallel. Testing of the Q2W and

Q4W dosing schedules in Part B can proceed concurrently with independent escalation decisions based upon review of the current total safety experience and following consultation and agreement between Investigators and the Sponsor. Treatment in Part B will be initiated after the decision is made to escalate to the third dose cohort in Part A (in accordance with dose escalation rules).

**Part A1** consists of cohort expansion with BMS-986016 monotherapy in 2 disease-restricted cohorts of approximately 6-12 subjects each. Treatment in Part A1 will be initiated at the MAD determined in Part A (ie, 800 mg). The dose selected for Part A1 will not exceed the MAD in Part A, but dose selection may change according to assessment of other data, including toxicities and PK and pharmacodynamic data from Parts A and A1. Subjects in Part A1 may cross over to combination therapy with nivolumab and BMS-986016 in sequential infusion if they meet predefined criteria.

**Part C** consists of cohort expansion in disease-restricted cohorts using a multistage approach, treated with sequential infusion of nivolumab and BMS-986016. Cohorts deemed futile (see sample size section for further details) at Stage 1 will be discontinued, whereas those deemed promising may be expanded further up to 90 to 120 subjects in total after careful evaluation of all available data, including the totality of efficacy, safety profile, and PK/pharmacodynamics. Otherwise, additional subjects may be treated to collect more data during Stage 2 in order to make decisions for further expansion. The doses selected for Part C will not exceed the Part B MTD or MAD, and specific doses selected may incorporate assessment of other data, including toxicities and PK and pharmacodynamic data from Parts A and B. Subjects in Part C cannot cross over to Part A1 either.

[figure not shown]
**Part D** consists of melanoma subjects who progressed on prior IO therapy. There is a Part D1 and a Part D2 within Part D. Most subjects in Part D will receive coadministration of BMS-986016 and nivolumab. Part D1 employs a focused set of eligibility criteria to build upon eligible subjects from the Part C melanoma prior IO cohort with the primary goal of testing the efficacy of 80 mg BMS-986016 + 240 mg nivolumab Q2W regimen. Enrollment may continue until the following criteria are met: (a) 90 efficacy-evaluable LAG-3-positive subjects have been treated, (b) 60 efficacy-evaluable LAG-3-positive and BRAF wild-type subjects have been treated, and (c) 60 efficacy-evaluable LAG-3-positive and ipilimumab-pretreated subjects have been treated. Part D1 will also have 2 other cohorts: 1) 160 mg BMS-986016 with 480 mg of nivolumab Q4W coadministration and 2) BMS-986213 (relatlimab 160 mg/nivolumab 480 mg) Q4W.

If subjects do not meet the more focused eligibility of Part D1, they may be eligible for Part D2, which is more flexible with respect to the allowed prior therapies and performance status. Part D2 will test safety and efficacy in this broader patient population and will employ the more convenient Q4W dosing in 2 different dose combinations (160 mg BMS-986016 + 480 mg nivolumab and subsequently 240 mg BMS-986016 + 480 mg of nivolumab). Adolescents (12 to < 18 years of age) weighing less than 40 kg will receive body weight-based dosing, equivalent to the conversion from a median adult weight of 80 kg (1 mg/kg BMS-986016 and 3 mg/kg of nivolumab Q2W, 2 mg/kg BMS-986016 and 6 mg/kg of nivolumab Q4W, or 6 mg/kg BMS-986016 and 6 mg/kg of nivolumab Q4W for corresponding fixed doses of 80/240 Q2W, 160/480 Q4W, and 240/480 Q4W, respectively). This adolescent dosing scheme also applies to BMS-986213. The doses and schedule

selected for Part D will not exceed the Part B MTD or MAD, and dosing of the cohorts may be altered in collaboration between the Investigators and Sponsor, based upon the overall ongoing study data, including evaluation of toxicities, PK, and pharmacodynamics. A schematic of the study is provided in Figure 1.

**Part E** consists of advanced melanoma participants. Two cohorts of melanoma participants will be enrolled in Part E: melanoma participants who experienced disease progression on prior anti-PD-1 therapy and melanoma participants who have not received prior systemic anticancer therapy for unresectable or metastatic melanoma. In Part E, melanoma participants will be administered either 160 mg BMS-986016 with 480 mg of nivolumab Q4W or 480 mg BMS-986016 with 480 mg of nivolumab Q4W; the specific dosing regimen will be dependent on 1) whether the subject had progressive disease on an earlier anti-PD-1 therapy and 2) randomization.

**Figure 1:** Study Schematic

[figure not shown]
Sequential = sequential administration of nivolumab first, followed by BMS-986016 infusion within 15 to 30 minutes of completing nivolumab infusion. For doses of 960 mg relatlimab + 480 mg nivolumab Q4W and higher doses, BMS-986016 infusion should be administered no sooner than 30 minutes following completion of nivolumab infusion.

IO = immuno-oncology agents (such as, but not limited to, anti-cytotoxic T lymphocyte-associated antigen 4 (CTLA-4), anti-PD-1, anti-PD-L1, anti-PD-L2, anti-KIR, anti-CD137, anti-LAG-3, and/or anti-OX40 antibodies).

[figure not shown]
\* Subsequent to site-specific amendment #15 (dated 13 August 2018), the dose escalation design was changed to BLRM-Copula from the 3 + 3 + 3 design.

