In Part D, melanoma prior immuno-oncology (IO) extended expansion cohorts, most subjects will receive coadministration of BMS-986016 and nivolumab in a single IV bag at 2 different select doses, either at Q2W or Q4W, in 8-week cycles; some subjects will receive BMS-986213 FDC product. Part D1 employs focused eligibility criteria to build upon eligible subjects from the Part C melanoma prior IO cohort. If subjects do not meet the more focused eligibility of Part D1, they may be eligible for Part D2, which is more flexible in the allowed prior therapies and performance

status. Part D2 will test safety and efficacy in this broader patient population and will employ the more convenient Q4W dosing in 2 different dose combinations.

In Parts C, D, and E, adolescents (12 to < 18 years of age) weighing less than 40 kg will be dosed based on weight (1 mg/kg BMS-986016 and 3 mg/kg of nivolumab Q2W, 2 mg/kg BMS-986016 and 6 mg/kg of nivolumab Q4W, and 6 mg/kg BMS-986016 and 6 mg/kg of nivolumab Q4W) up to maximum doses of the respective adult flat doses.

In Part E advanced melanoma, exposure response evaluation cohorts, subjects will receive coadministration of BMS-986016 and nivolumab in a single IV bag at different select doses, Q4W, in 8-week cycles.

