both study drugs are given as sequential infusion, nivolumab will be given first, followed by BMS-986016 within 15 to 30 minutes of completing the infusion of nivolumab. In Part B, for doses of 960 mg relatlimab + 480 mg nivolumab Q4W and higher doses, BMS-986016 infusion should be administered no sooner than 30 minutes following completion of nivolumab infusion. Part D, the melanoma prior IO extended expansion, will have 2 sections: Part D1 will have a focused eligibility criteria with a cohort of 80 mg of BMS-986016 with 240 mg nivolumab Q2W, a cohort of 160 mg BMS-986016 with 480 mg of nivolumab Q4W, and a cohort of BMS-986213 (160 mg relatlimab/480 mg nivolumab) Q4W; Part D2 will have an expanded eligibility criteria with 2 cohorts in sequence: 160 mg BMS-986016 with 480 mg of nivolumab Q4W and 240 mg BMS-986016 and 480 mg of nivolumab Q4W. In Part D, study drugs are given as a coadministration or single infusion of BMS-986213 over approximately 60 minutes. In Part E, melanoma subjects will be administered either 160 mg BMS-986016 with 480 mg of nivolumab Q4W or 480 mg BMS-986016 with 480 mg of nivolumab Q4W; the specific dosing regimen will be dependent on whether the subject previously received anti-PD-1 therapy in the advanced, unresectable, or metastatic setting and had progressive disease on that earlier treatment regimen and randomization, as previously described. Adolescents (12 to < 18 years of age) weighing less than 40 kg will be dosed based on weight (1 mg/kg BMS-986016 and 3 mg/kg of nivolumab Q2W, 2 mg/kg BMS-986016 and 6 mg/kg of nivolumab Q4W, or 6 mg/kg BMS-986016 and 6 mg/kg of nivolumab Q4W). In Parts C, D, and E, Q4W dosing, BMS-986016 and nivolumab will be

administered on Days 1 and 29 of each treatment cycle; visits will occur every 2 weeks to assess safety for the first cycle of treatment, and thereafter visits will only be on Day 1 and Day 29 of each subsequent cycle. [REDACTED]

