### **1.1.9.8 Dose Rationale for Adolescents**

The PK of drugs and many therapeutics proteins has been shown to be similar between adolescents and adults once the effect of body size on PK is taken into consideration. Therefore, in general, adult doses would be expected to achieve similar systemic exposures in adolescents. In this study, BMS-986016 in combination with nivolumab was administered as a flat dosing in adults; therefore, a minimum body weight threshold in adolescents ( $\geq 40$  kg) is defined to receive the same adult flat dose to prevent exceeding target adult exposures. Adolescent subjects  $< 40$  kg body weight will be given body weight-based dosing, equivalent to the conversion from a median adult weight of 80 kg. Therefore, the weight-based doses are 1 mg/kg BMS-986016 and 3 mg/kg nivolumab Q2W, 2 mg/kg BMS-986016 and 6 mg/kg nivolumab Q4W, and 6 mg/kg BMS-986016 and 6 mg/kg nivolumab Q4W for corresponding fixed doses of 80/240 Q2W, 160/480 Q4W, and 480/480 Q4W, respectively. This adolescent dosing scheme also applies to BMS-986213.

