**Part D** consists of melanoma subjects who progressed on prior IO therapy. There is a Part D1 and a Part D2 within Part D. Most subjects in Part D will receive coadministration of BMS-986016 and nivolumab. Part D1 employs a focused eligibility to build upon eligible subjects from the Part C melanoma prior IO cohort, with the primary goal of testing the efficacy of 80 mg BMS-986016 + 240 mg nivolumab Q2W. Enrollment may continue until the following criteria are met: (a) 90 efficacy-evaluable LAG-3-positive subjects have been treated, (b) 60 efficacy-evaluable LAG-3-positive and BRAF wild-type (WT) subjects have been treated, and (c) 60 efficacy-evaluable LAG-3-positive and ipilimumab pretreated subjects have been treated. Part D1 will also have 2 other cohorts: 1) 160 mg BMS-986016 with 480 mg of nivolumab Q4W coadministration and 2) a cohort of BMS-986213 (relatlimab 160 mg/nivolumab 480 mg) Q4W. If subjects do not meet the more focused eligibility of Part D1, they may be eligible for Part D2, which is more flexible with respect to the allowed prior therapies and performance status. Part D2 will test safety and efficacy in this broader patient population and will employ the more convenient Q4W dosing in 2 different dose combinations (160 mg BMS-986016 + 480 mg nivolumab, and subsequently, 240 mg BMS-986016 + 480 mg of nivolumab). Adolescents (12 to < 18 years of age) weighing less than 40 kg will receive weight-based dosing (see [Section 1.1.9.8](#)). The doses and schedule selected for Part D will not exceed the Part B MTD or MAD, and dosing of the cohorts may be altered in collaboration between the Investigators and Sponsor, based upon the overall ongoing study data, including toxicities, PK, and pharmacodynamics. A schematic of Part D is provided in [Figure 3.1-2](#).

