Adolescents (12 to < 18 years of age) weighing less than 40 kg will be dosed based on weight (1 mg/kg BMS-986016 and 3 mg/kg nivolumab Q2W, 2 mg/kg BMS-986016 and 6 mg/kg nivolumab Q4W, or 6 mg/kg BMS-986016 and 6 mg/kg nivolumab Q4W. In Parts C, D, and E, Q4W dosing, BMS-986016 and nivolumab will be administered on Days 1 and 29 of each treatment cycle; visits will occur every 2 weeks to assess safety for the first cycle of treatment, and thereafter visits will only be on Day 1 and Day 29 of each subsequent cycle. [REDACTED]

Tumor

response will be evaluated using RECIST v1.1.

Subjects will be allowed to continue study therapy until the first occurrence of either 1) PD, 2) clinical deterioration, and/or 3) meeting other criteria for discontinuation. Refer to [Section 3.5](#) for additional details. Treatment beyond progression should be considered in select participants with initial RECIST v1.1-defined PD who are receiving clinical benefit as assessed by the Investigator, tolerating treatment, and meeting other criteria specified in [Section 4.3.4](#). Follow-up imaging should be obtained to confirm progression where appropriate (see [Section 5.1](#)). Subjects who discontinue treatment will enter a 135-day **Clinical Follow-up** period.

After completion of the Clinical Follow-up period, subjects enter the **Survival Follow-up** period. During this period, clinic visits or telephone contact every 12 weeks will be performed to assess survival status. Survival follow-up visits will be scheduled based on the last clinical follow-up visit. **Diagnostic imaging must be performed every 8 weeks until disease progression. For subjects who discontinue treatment at the Investigator's discretion with a CR, PR, or stable disease (SD) by RECIST v1.1, imaging must be performed every 12 weeks until disease progression.** The duration of this period may continue for up to 5 years from the first dose.

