If subjects do not meet the more focused eligibility of Part D1, they may be eligible for Part D2, which is more flexible with respect to the allowed prior therapies and performance status. Part D2 will test safety and efficacy in this broader patient population and will employ the more convenient Q4W combination coadministration dosing. Initial dosing will be 160 mg BMS-986016 + 480 mg nivolumab. Once further safety is established at the BMS-986016 160 mg + nivolumab 480 mg dose (see [Section 8.1.4](#)), subsequently enrolled subjects may be treated with BMS-986016 240 mg + nivolumab 480 mg. The doses and schedule selected for Part D will not exceed the Part B MTD or MAD, and dosing of the cohorts may be altered in collaboration between the Investigators and Sponsor, based upon the overall ongoing study data, including toxicities, PK, and pharmacodynamics.

There will be no dose adjustments for individual subjects. Expansion cohorts in Part D will be restricted to advanced melanoma subjects ([Section 3](#)). Efficacy analyses are described in [Section 8.4.2](#).

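### The synopsis gives adolescents under 40 kg on the Part D2 240/480 mg Q4W regimen twice the relatlimab per kg that its own 80-kg conversion implies; the correct 3/6 mg/kg appears in no operative section

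*Combined protocol and SAP*

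**What the plan says.** The Synopsis (Study Design, Part D) sets the rule for adolescents under 40 kg: they "will receive body weight-based dosing, equivalent to the conversion from a median adult weight of 80 kg". It then lists three weight-based doses and matches them in order to three flat doses. The last part of the list reads "6 mg/kg BMS-986016 and 6 mg/kg of nivolumab Q4W for corresponding fixed doses of 80/240 Q2W, 160/480 Q4W, and 240/480 Q4W, respectively".

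Section 1.1.9.8 (Dose Rationale for Adolescents) states the same 80-kg rule and the same three mg/kg pairs, but its last match is different: "6 mg/kg BMS-986016 and 6 mg/kg nivolumab Q4W for corresponding fixed doses of 80/240 Q2W, 160/480 Q4W, and 480/480 Q4W, respectively". It has no entry for 240/480 mg.

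The other current dose lists name no flat doses and give only 1/3, 2/6 and 6/6 mg/kg:

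- Synopsis, investigational products, which adds a cap: "6 mg/kg BMS-986016 and 6 mg/kg of nivolumab Q4W) up to maximum doses of the respective adult flat doses".
- Synopsis, treatment period text below the Part E figure: "2 mg/kg BMS-986016 and 6 mg/kg of nivolumab Q4W, or 6 mg/kg BMS-986016 and 6 mg/kg of nivolumab Q4W".
- Section 3.1, below Figure 3.1-3: "2 mg/kg BMS-986016 and 6 mg/kg nivolumab Q4W, or 6 mg/kg BMS-986016 and 6 mg/kg nivolumab Q4W".

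For Part D, Section 3.1 says adolescents "weighing less than 40 kg will receive weight-based dosing" and sends the reader to Section 1.1.9.8. Section 3.1.2.5 keeps 240/480 mg as a Part D2 regimen: once safety at 160/480 mg is established, "subsequently enrolled subjects may be treated with BMS-986016 240 mg + nivolumab 480 mg". Section 3.3.1, criterion 3(a), admits subjects from age 12 to Part D where local rules allow.

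**The concern.** The synopsis states a conversion rule and then gives a dose that breaks it. The same mg/kg pair is matched to 240/480 mg in the synopsis and to 480/480 mg in Section 1.1.9.8, and both cannot follow from one rule.

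This is more than a duplicated typing error, because 240/480 mg is a current Part D2 regimen open to adolescents. A site looking up the weight-based dose for that regimen finds one explicit value in the protocol, the one in the synopsis. Section 1.1.9.8, to which Section 3.1 refers for Part D, is silent on 240/480 mg. What is at stake is the relatlimab dose of any subject under 40 kg on that regimen. No sample size, power or error rate is involved.

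**Working it through.** **Inputs.** Reference weight 80 kg (Synopsis, Study Design; Section 1.1.9.8). Weight-based pairs 1/3, 2/6 and 6/6 mg/kg (same places). Part D2 flat dose 240/480 mg (Section 3.1.2.5). Cap at the adult flat dose (Synopsis, investigational products).

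**Step 1: reproduce the synopsis matches.** Flat dose = mg/kg × 80 kg.

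| Relatlimab/nivolumab, mg/kg | × 80 kg | Synopsis | Section 1.1.9.8 |
|---|---|---|---|
| 1/3 Q2W | 80/240 mg | 80/240 | 80/240 |
| 2/6 Q4W | 160/480 mg | 160/480 | 160/480 |
| 6/6 Q4W | 480/480 mg | **240/480** | 480/480 |

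Two synopsis matches reproduce. In the third, the nivolumab half is right (6 × 80 = 480) and the relatlimab half is wrong (6 × 80 = 480, not 240).

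**Step 2: convert the Part D2 regimen.** 240/80 = 3 mg/kg relatlimab and 480/80 = 6 mg/kg nivolumab, so the rule gives 3/6 mg/kg. The only mention of that pair is in Appendix 7, which records its removal at Revised Protocol 11. That is superseded text and supplies no current dose.

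**Step 3: size of the difference.** The weights are assumed for illustration; the documents show no subject under 40 kg. The former exclusion of adolescents under 30 kg (Section 3.3.2, criterion 2q) is marked not applicable, so 25 kg is included.

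| Weight | Relatlimab at 6 mg/kg (synopsis) | Relatlimab at 3 mg/kg (80-kg rule) |
|---|---|---|
| 25 kg | 150 mg | 75 mg |
| 30 kg | 180 mg | 90 mg |
| 35 kg | 210 mg | 105 mg |
| 39 kg | 234 mg | 117 mg |

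The ratio is 6/3 = 2 at every weight. Nivolumab is the same either way (at 30 kg, 6 × 30 = 180 mg).

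**Step 4: does the cap catch it?** At 6 mg/kg the 240 mg cap is reached at 240/6 = 40 kg, where weight-based dosing ends. Below 40 kg it never binds.

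**Step 5: comparison with the other regimens.** Share of the adult flat relatlimab dose at 39 kg:

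- 1 mg/kg for 80 mg: 39/80 = 48.75%
- 2 mg/kg for 160 mg: 78/160 = 48.75%
- 6 mg/kg for 480 mg: 234/480 = 48.75%
- 3 mg/kg for 240 mg (corrected): 117/240 = 48.75%
- 6 mg/kg for 240 mg (synopsis): 234/240 = 97.5%

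Only the synopsis pair departs from the common share.

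**The case against.** The strongest reply is that this is a single wrong number in a synopsis and that no harm is shown. The rule is stated identically in the synopsis and in Section 1.1.9.8, so a careful reader can derive 3/6 mg/kg in one step. Sections 4.1 and 4.1.3 leave preparation and administration details to separate site and pharmacy materials, which may carry the right value. Appendix 7 (Revised Protocol 11) records that 6/6 mg/kg was meant to correspond to 480/480 mg, so the intent is not in doubt. Appendix 7 (Amendment 14) puts the close of enrollment at 30-Jul-2021.

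The synopsis dose also stays below the cohort's 240 mg adult flat dose. It equals the mg/kg that a 40-kg adolescent receives on the flat dose (240/40 = 6), and it is the accepted adolescent dose for 480/480 mg. Section 1.4.1.4.2 reports no maximum tolerated dose reached up to 960/480 mg Q4W.

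Most of this stands, and it limits the weight of the point: it is a text inconsistency, practical exposure may be nil, and no safety harm is claimed. It does not make the text right. The site materials cannot be seen from here, and the section to which Part D readers are sent has no 240/480 mg entry. Closed enrollment does not fully dispose of the matter either, because Table 5.1-2 (footnote c) allows treatment past 5 years under the original dose and rules.

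**Conclusion.** The concern holds: the synopsis is wrong as written. Under its own 80-kg rule, 6/6 mg/kg corresponds to 480/480 mg, and the Part D2 regimen of 240/480 mg corresponds to 3/6 mg/kg, which no current operative section lists. Read literally, the synopsis doubles relatlimab for a Part D2 subject under 40 kg assigned to 240/480 mg, and the cap does not prevent it.

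The factor of 2 follows from the documents alone. The milligram figures rest on assumed body weights. Whether anyone was dosed this way is unknown. The point should be corrected because it is an explicit paediatric dose and the correction costs almost nothing. It does not affect the design, the analysis or any statistical figure.

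**What to change.** In the Synopsis (Study Design, Part D), replace the three-pair list with four: 1/3 mg/kg for 80/240 mg Q2W, 2/6 for 160/480 mg Q4W, 3/6 for 240/480 mg Q4W and 6/6 for 480/480 mg Q4W. The 480/480 mg regimen belongs to Part E, so label each pair with the parts it serves. Add 3/6 mg/kg for 240/480 mg to Section 1.1.9.8 and to the lists in the synopsis (investigational products; treatment period) and Section 3.1.

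Check the dosing records of any Part D2 subject under 40 kg assigned to 240/480 mg; there may be none. If one is still on treatment at 6 mg/kg, the sponsor should decide and document the handling, since Section 4.3.1.2 generally bars dose reduction within a subject.

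As a separate minor edit, the Part E sentence in Section 3.1 below Figure 3.1-3 gives the higher relatlimab dose as 240 mg where the Part E objective, arms and sample size say 480 mg. Correct it to 480 mg; no Part E record audit or sensitivity analysis is needed.

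The cost is an administrative letter, or an item in the next amendment, plus the narrow record check. No design or analysis change is needed.

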**Figure 2:** **Part D**

**Part D: Melanoma prior IO Extended Expansion**

**Figure 3:** **Part E**

Part E consists of advanced melanoma participants. Two cohorts of melanoma participants will be enrolled in Part E: melanoma participants who experienced disease progression on prior anti-PD-1 therapy and melanoma participants who have not received prior systemic anticancer therapy for unresectable or metastatic melanoma.

Melanoma participants who experienced disease progression on prior anti-PD-1 therapy will all receive 480 mg BMS 986016 + 480 mg nivolumab Q4W dose regimen.

Melanoma participants who have not received prior systemic anticancer therapy for unresectable or metastatic melanoma will be randomized to 1 of the 2 following treatment arms:

160 mg BMS-986016 + 480 mg nivolumab Q4W

480 mg BMS 986016 + 480 mg nivolumab Q4W

Subjects will complete up to 4 periods of the study: **Screening** (up to 28 days), **Treatment**, **Clinical Follow-up** (135 days), and **Survival Follow-up** (up to 5 years following the first dose of study drug). Two independent periods, **Crossover** and **Rechallenge** may be conducted in selected cases at progression. **As of Protocol Amendment 14, rechallenge is not permitted.**

In the **Treatment Period**, each treatment cycle comprises 4 doses of either BMS-986016 alone (Parts A and A1) or in combination with nivolumab (Part B and C except bladder cohort), administered on Days 1, 15, 29, and 43 of each treatment cycle. [REDACTED]

[REDACTED] . In Parts B and C when

both study drugs are given as sequential infusion, nivolumab will be given first, followed by BMS-986016 within 15 to 30 minutes of completing the infusion of nivolumab. In Part B, for doses of 960 mg relatlimab + 480 mg nivolumab Q4W and higher doses, BMS-986016 infusion should be administered no sooner than 30 minutes following completion of nivolumab infusion. Part D, the melanoma prior IO extended expansion, will have 2 sections: Part D1 will have a focused eligibility criteria with a cohort of 80 mg of BMS-986016 with 240 mg nivolumab Q2W, a cohort of 160 mg BMS-986016 with 480 mg of nivolumab Q4W, and a cohort of BMS-986213 (160 mg relatlimab/480 mg nivolumab) Q4W; Part D2 will have an expanded eligibility criteria with 2 cohorts in sequence: 160 mg BMS-986016 with 480 mg of nivolumab Q4W and 240 mg BMS-986016 and 480 mg of nivolumab Q4W. In Part D, study drugs are given as a coadministration or single infusion of BMS-986213 over approximately 60 minutes. In Part E, melanoma subjects will be administered either 160 mg BMS-986016 with 480 mg of nivolumab Q4W or 480 mg BMS-986016 with 480 mg of nivolumab Q4W; the specific dosing regimen will be dependent on whether the subject previously received anti-PD-1 therapy in the advanced, unresectable, or metastatic setting and had progressive disease on that earlier treatment regimen and randomization, as previously described. Adolescents (12 to < 18 years of age) weighing less than 40 kg will be dosed based on weight (1 mg/kg BMS-986016 and 3 mg/kg of nivolumab Q2W, 2 mg/kg BMS-986016 and 6 mg/kg of nivolumab Q4W, or 6 mg/kg BMS-986016 and 6 mg/kg of nivolumab Q4W). In Parts C, D, and E, Q4W dosing, BMS-986016 and nivolumab will be

administered on Days 1 and 29 of each treatment cycle; visits will occur every 2 weeks to assess safety for the first cycle of treatment, and thereafter visits will only be on Day 1 and Day 29 of each subsequent cycle. [REDACTED]

[REDACTED] Tumor response will be evaluated using RECIST v1.1. Subjects will be allowed to continue study therapy until the first occurrence of either: 1) progressive disease (PD), 2) clinical deterioration, and/or 3) meeting other criteria for discontinuation ([Section 3.5](#)). Treatment beyond progression may be allowed in select subjects with initial RECIST v1.1-defined PD who are receiving clinical benefit as assessed by the Investigator, tolerating treatment, and meeting other criteria specified in [Section 4.3.4](#). Subjects who discontinue treatment will enter a 135-day **Clinical Follow-up** period.

[figure not shown]
After completion of the **Clinical Follow-up** period, subjects will enter the **Survival Follow-up** period. During this period, clinic visits or telephone contact every 12 weeks will be performed to assess survival status. Survival follow-up visits will be scheduled based on the last clinical follow-up visit. The duration of this period may continue for up to 5 years from the first dose. **Diagnostic imaging must be performed every 8 weeks until disease progression. For subjects who discontinue treatment at the Investigator's discretion with a complete response (CR), partial response (PR), or stable disease (SD) by RECIST v1.1, imaging must be performed every 12 weeks until disease progression.** If subjects progress during the Clinical Follow-up period or the Survival Follow-up period, they could further receive therapy with BMS-986016 alone or in combination therapy (**Rechallenge** period) as long as the benefit-risk ratio is considered favorable by the Investigator and the Medical Monitor and eligibility criteria are met ([Section 3.1.2.4](#)). The rechallenge-eligible Survival Follow-up period may continue for up to 5 years from the first dose of study drug. The original dose and schedule and protocol rules would apply accordingly. Subjects will not be rechallenged a second time. Collection of archival tissue (baseline) and tumor biopsies (baseline and on-treatment) will be optional for subjects enrolled for rechallenge. PK and biomarker monitoring will be limited ([Sections 5.5](#) and [5.7](#)). **As of Protocol Amendment 14, rechallenge is not permitted.** All subjects who discontinue primary study treatment following implementation of Protocol Amendment 14 will not be eligible for rechallenge. Subjects currently receiving rechallenge treatment will be allowed to continue, and subjects currently in the rechallenge-eligible Survival Follow-up as of this Protocol Amendment remain eligible for rechallenge.

For patients remaining on treatment beyond 5 years, subjects may continue on study treatment, as long as the benefit-risk ratio is considered favorable by the Investigator and continues to meet the criteria outlined in the protocol.

Also, subjects receiving therapy with BMS-986016 alone in expansion Part A1 may **cross over** to combination therapy at confirmed progression ([Section 3.1.2.1](#)).

A study schematic is shown in Figure 4.

**Figure 4:** Detailed Study Schematic

 Treatment beyond progression may be considered in select subjects as described in [Section 4.3.4](#).

 Diagnostic imaging must be performed every 8 weeks until disease progression, and in subjects who discontinue study treatment at the Investigator's discretion with a CR, PR, or SD via RECIST 1.1, imaging must be performed every 12 weeks until disease progression.

 For treatment visits in Parts B and C where BMS-986016 and nivolumab are administered sequentially, nivolumab will be administered first over 30 minutes, followed by BMS-986016 administration within 15 to 30 minutes after completion of the nivolumab infusion. For doses of 960 mg relatlimab + 480 mg nivolumab Q4W, BMS-986016 infusion should be administered no sooner than 30 minutes following completion of nivolumab infusion.

 Note the 6-week DLT period will be initiated with the 960 mg BMS-986016 dose level.

Note: As of Protocol Amendment 14, rechallenge is not permitted.

